6.1.3 Visit 00C, Day -28 to -14, Baseline Rectal Mucosal Biopsy, Clinic Visit

This visit will only take place for subjects being enrolled in the rectal biopsy cohort. The following activities will be performed at Visit 00C.

- Ensure participant is safe to proceed with biopsy procedure, including results of all clinical screening lab evaluations*.

*If the initial safety labs are >28 days old, these tests will need to be repeated and results obtained before rectal mucosal biopsy (see [Section 7.2](#)).

- Review medical history and any updates obtained by interview of subjects since the last screening visit (Visit 00A or, if performed, Visit 00B) to assure the participant is safe to proceed with biopsy procedure.
- Review interim sexual history to identify any new sexual partners since the last screening visit
- Review all concomitant medications and recent (within 28 days) vaccinations with subjects before the first vaccination for accuracy and completeness. Any new medications taken since the last screening visit (Visit 00A or, if performed, Visit 00B) will be recorded on the appropriate eCRF and reviewed to assure the participant is safe to proceed with biopsy procedure.
- Assess all AE/SAEs from the biopsy procedure and record them on the appropriate Electronic Case Report Form (eCRF).

- Obtain vital signs including oral temperature, blood pressure, and pulse to assure the participant is safe to proceed with biopsy procedure. Vital signs obtained on the day of biopsy will not be considered "screening", nor used for determining eligibility.
- Perform a targeted physical examination as needed before the biopsy procedure, if indicated based on review of complete medical history and updates obtained by interview of subjects since the last screening visit (Visit 00A or, if performed, Visit 00B).
- Perform rigid sigmoidoscopy and collect rectal mucosal biopsy samples for immunologic assays as described in the Schedule of Events ([Appendix A](#)) (for subjects in the mucosal biopsy subgroup).
- Subjects will be counseled not to engage in anal intercourse for 1 week after the rectal biopsy procedure.
- Subjects will be reminded to abstain from receptive anal and/or vaginal intercourse, insertion of anything into their vagina and/or anus, or oral sex for at least 2 days prior to the enrollment/first vaccination visit.

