5.1 Eligibility Criteria

5.1.1 Subject Inclusion Criteria

Subjects must meet all the following inclusion criteria to be eligible for this trial:

1. Must be aged 18-49 years old (inclusive) at the time of vaccination.
2. Must be able to provide written informed consent.
3. Must have a body mass index (BMI) ≥ 18.5 and $< 35.0 \text{ kg/m}^2$

4. Must be in good health based on physical examination, vital signs*, medical history, safety labs** (as applicable to the rectal biopsy and no biopsy cohorts) and the investigator's clinical judgment.

**Vital signs must be within the normal ranges in [Appendix C](#) If a subject has elevated systolic or diastolic blood pressure, subject may rest for 10 minutes in a quiet room and the blood pressure may be retaken.*

***Safety labs must be within the normal ranges in [Appendix C](#), and the normal ranges will be those used by the reference clinical lab.*

5. For female subjects only: If a female participant is of childbearing potential*, she must use contraception** from 30 days before study product administration through the end of study participation.

**A woman is considered of childbearing potential unless post-menopausal (defined as history of ≥ 1 year of spontaneous amenorrhea), or permanently surgically sterilized (bilateral oophorectomy, salpingectomy, hysterectomy).*

***Acceptable methods of contraception include: abstinence or no sex with a male, monogamous relationship with a man who had a vasectomy at least 6 months before the 1st study vaccine, prescription oral contraceptives, intrauterine device (IUD), birth control implants or injections, contraceptive patch, vaginal ring, condoms and diaphragms/cervical cap with spermicide (“double barrier” method)*

6. Must be available and willing to participate for the duration of this trial.
7. Willing to provide mucosal samples: vaginal secretions for women and oropharyngeal and rectal secretions for men and women.
8. For the rectal biopsy cohort only, willing to provide rectal biopsies.

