6 STUDY PROCEDURES

6.1 Screening

6.1.1 Visit 00A, Day -56 to -1 for subjects in the no biopsy cohort / -56 to -28 for subjects in the biopsy cohort, 1st Screen, Clinic Visit

Potential subjects will be screened for eligibility up to 56 days before the first study vaccination. The following activities will be performed at the 1st screening visit.

- Begin the informed consent process. Provide subjects with a description of this trial (purpose and study procedures) and ask them to read the ICF. Provide an opportunity to the potential subject to ask questions. If she/he wishes to proceed with participation, the ICF should be signed before performing any screening procedures
- Review eligibility criteria.
- Interview subjects to collect demographics, medical history, sexual history, vaccination history, and pre-study medication use. Interview of subjects is sufficient for obtaining medical history. Solicitation of medical records from the subject's primary care provider is not required.
- Review subjects' concomitant medications taken within 30 days before signing the ICF.
- Obtain vital signs, including oral temperature, pulse, and blood pressure to assure eligibility.
- Measure height and weight and calculate BMI.
- Perform a physical examination including the following organs and organ systems: general appearance, head/eyes/ears/nose/throat (HEENT), neck, lungs, heart, abdomen, extremities, musculoskeletal, lymph nodes, skin, and nervous system. Genital and rectal exams will be performed at the investigator's discretion. All physical exams will be done by a clinician licensed to make medical diagnoses and listed on Form FDA 1572 as site PI or sub-investigator
- Collect venous blood for RPR and HIV-1/2 antibody testing.
- During screening for the rectal biopsy cohort only, collect venous blood for complete blood count (White Blood Count (WBC), hemoglobin, Platelet Count (PLT)), prothrombin time (PT) and activated partial thromboplastin time (aPTT)

- Collect urine for pregnancy test from all female subjects of childbearing potential.
- Collect pharyngeal and rectal swabs for nucleic acid amplification testing (NAAT) for GC and CT
- Collect urine for NAAT for GC/CT from male subjects
- Collect a self-collected vaginal swab for NAAT for GC/CT/Trichomonas from female subjects

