- The overall eligibility of the subject to participate in this trial will be assessed once all screening test values and results of any other required evaluations are available. Subjects who qualify for inclusion will be contacted and scheduled for baseline rectal mucosal biopsy or first vaccination within 28 days.
- Subjects who qualify for inclusion in the rectal biopsy cohort will be instructed to abstain from receptive anal intercourse or insertion of anything into their anus, for at least 2 days prior to the baseline rectal mucosal biopsy visit
- Subjects who qualify for inclusion will be instructed to abstain from receptive anal and/or vaginal intercourse, insertion of anything into their vagina and/or anus, or oral sex for at least 2 days prior to the enrollment/first vaccination visit

6.1.2 Visit 00B, Day -7 to -1 for subjects in the no biopsy cohort / -34 to -28 for subjects in the biopsy cohort, 2nd Screen, Clinic Visit (optional)

This screening visit will only occur to repeat a screening assessment whose initial result is thought to be temporary). The following activities will be performed at the 2nd screening visit if it occurs.

- Review eligibility criteria, including results of available clinical screening lab evaluations.
- Review medical history and any updates obtained by interview of subjects since the screening visit (Visit 00A) to assure continued eligibility.
- Review interim sexual history to identify any new sexual partners since the last screening visit
- Review all concomitant medications recorded on the appropriate Electronic Case Report Form (eCRF).

- Obtain vital signs including oral temperature, blood pressure, and pulse, if needed.
- Measure height and weight and calculate BMI, if needed.
- Perform a targeted physical examination, if needed.
- Collect blood and urine for safety labs, if needed
- Subjects who qualify for inclusion in the rectal biopsy cohort will be instructed to abstain from receptive anal intercourse or insertion of anything into their anus, for at least 2 days prior to the baseline rectal mucosal biopsy visit

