8.4 Type and Duration of Follow-up of Subjects after Adverse Events

AEs will be assessed, and followed from initial recognition of the AE through end of the protocol defined follow-up period.

SAEs will be followed up through resolution even if duration of follow-up goes beyond the protocol-defined follow-up period.

Resolution of an AE is defined as the return to pre-treatment status or stabilization of the condition with the expectation that it will remain chronic.

8.5 Procedures to be Followed in the Event of Abnormal Laboratory Test Values or Abnormal Clinical Findings

The site PI or appropriate sub-investigator is responsible for recording all AE/SAEs that are observed or reported during this trial, regardless of the relationship to the vaccine. AE/SAEs or abnormal clinical findings will be collected, assessed, documented, reported, and followed appropriately.

All subjects will be screened for GC and CT infection at all relevant mucosal sites with NAAT at screening (Visit 00A) and prior to rectal mucosal sampling procedures at Day 29 (Visit 04) and at the final study visit (Day 181 (Visit 08)). Female subjects will also be screened for *Trichomonas vaginalis* infection with NAAT at screening (Visit 00A). Subjects will also be screened for RPR at screening (Visit 00A), Day 29 (Visit 04) and Day 181 (Visit 08), as well as HIV-1/2 antibody (Visit 00A and 08). If a positive result on any of these screening tests occurs, the subject will be referred for appropriate follow-up and results reported as required by state law.

Safety labs will only be required at screening in the rectal biopsy cohort. Safety labs may be repeated during the study at the investigator's discretion as part of the assessment of abnormal clinical findings.

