| Hypotension (systolic) mmHg | 85 – 89 | 80 – 84 | <80 |
| Hypotension (diastolic) mmHg | 50 – 54 | 45 – 49 | <45 |
| Hypertension (systolic) mmHg | 141 – 150 | 151 – 155 | >155 |

| | | | |
|-------------------------------|---------|----------|------|
| Hypertension (diastolic) mmHg | 91 – 95 | 96 – 100 | >100 |
|-------------------------------|---------|----------|------|

Pulse and blood pressure assessed on Day 1 prior to the first study vaccination will be considered as baseline.

Clinical safety laboratory results* will be graded as follows:

Clinical Safety Laboratory Adverse Event*

| Hematology | Normal Range | Mild (Grade 1) | Moderate (Grade 2) | Severe (Grade 3) |
|---|--------------|-------------------|-----------------------|---------------------|
| WBC $10^3/\mu\text{L}$ (Low) | 3.8 – 10.8 | 2.5 – 3.7 | 1.5 – 2.4 | <1.5 |
| WBC $10^3/\mu\text{L}$ (High) | 3.8 – 10.8 | 10.9 – 15.0 | 15.1 – 20.0 | >20.0 |
| Hgb g/dL (Low) (Female) | 11.7 – 15.5 | 11.0 – 11.6 | 9.5 – 10.9 | <9.5 |
| Hgb g/dL (Low) (Male) | 13.2 – 17.1 | 12.0 – 13.1 | 10.0 – 11.9 | <10.0 |
| Platelets $10^3/\mu\text{L}$ (Low) | 140 – 400 | 125 – 139 | 100 – 124 | <100 |
| Platelets $10^3/\mu\text{L}$ (High) | 140 – 400 | 401 – 550 | 551 – 750 | >750 |
| PT (seconds) (increase by factor) (prothrombin time) | 9.0 – 11.5 | >1.0 – 1.1 x ULN | >1.1 – 1.2 x ULN | > 1.2 x ULN |
| aPTT (seconds) (increase by factor) (activated partial thromboplastin time) | 22.0 – 34.0 | >1.0 – 1.2 x ULN | >1.2 – 1.4 x ULN | >1.4 x ULN |

*Clinical laboratory evaluations assessed at the screening visit will be considered as baseline

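### No pregnancy test is required at the baseline rectal biopsy (Visit 00C), and up to 26 days after the screening test can pass with neither a repeat test nor required contraception

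*Protocol*

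**What the plan says.** **Tests.** At Visit 00A, Protocol Section 6.1.1 says "Collect urine for pregnancy test from all female subjects of childbearing potential". Section 7.2.1 names two pregnancy tests before the first dose: that one, and one within 24 hours before the Day 1 vaccination. The second must be negative, and known, before randomization. The test before dose 2 is on the same 24-hour footing.

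**Biopsy visit.** Section 6.1.3 lists the Visit 00C activities: a safety check ("Ensure participant is safe to proceed with biopsy procedure, including results of all clinical screening lab evaluations"), updated medical and sexual history, medications, vital signs, a targeted examination if indicated, and the sigmoidoscopy. No pregnancy test is listed. The pregnancy rows of Protocol Appendix A and SAP Table 2 show a required entry at Visit 00A, a discretionary one at the optional Visit 00B, and nothing further until Visit 1.

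**Contraception.** Inclusion criterion 5 requires it "from 30 days before study product administration through the end of study participation".

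**Repeat rule.** Section 6.1.3 adds: "If the initial safety labs are >28 days old, these tests will need to be repeated and results obtained before rectal mucosal biopsy".

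**Scheduling.** Section 6.1.1 says: "Subjects who qualify for inclusion will be contacted and scheduled for baseline rectal mucosal biopsy or first vaccination within 28 days".

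**Pregnancy as a bar.** Pregnancy is exclusion criterion 24. Section 8.3.3 stops further study procedures, not only vaccination, in subjects who become pregnant.

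**The concern.** Before each injection the plan insists on a pregnancy result less than a day old. Before the first biopsy it accepts one that may be weeks old, although the procedure is done purely for research and takes 8 to 12 specimens through a rigid sigmoidoscope (Section 7.1.1). A pregnancy not present or not detectable at Visit 00A would next be looked for on Day 1, when exclusion 24 can no longer prevent the biopsy.

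The stake is that the trial's own pregnancy exclusion may be applied too late for one procedure. No pregnancy-specific risk of the biopsy is asserted, no probability of pregnancy is estimated, and no bias in a primary or secondary endpoint is claimed. A subject lost on Day 1 may be replaced (Section 5.2.2), and the biopsy assays are exploratory.

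**Working it through.** **Inputs**

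- Screening test day *s*: Day -56 to -28 (Section 6.1.1, biopsy cohort).
- Biopsy day *b*: Day -28 to -14 (Section 6.1.3).
- Contraception start: 30 days before Day 1. The day numbering has no Day 0 (SAP Listing 7 note), so this is Day -30.
- Women in the biopsy cohort: 8 + 2 = 10 (Table 1).

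The documents give no figure of their own for this interval, so there is none to reproduce.

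**Formulas and results**

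1. Age of the last required result at biopsy = *b* - *s*. Maximum: -14 - (-56) = 42 days.
2. Days after the test with neither a repeat nor required contraception = max(0, -30 - *s*). Maximum: -30 - (-56) = 26 days. It is 0 when *s* is Day -30 or later.
3. Days of required contraception before the biopsy = *b* + 30: 2 days at *b* = -28 and 16 days at *b* = -14. Check on the longest case: 26 + 16 = 42.
4. Biopsy to the next required test on Day 1: 14 to 28 days.

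**If the repeat rule covers the pregnancy test**, the age is limited to 28 days. The earliest test that then needs no repeat gives:

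| Biopsy day | Earliest test day | Age | Uncovered days | Contraception days |
|---|---|---|---|---|
| -28 | -56 | 28 | 26 | 2 |
| -21 | -49 | 28 | 19 | 9 |
| -14 | -42 | 28 | 12 | 16 |

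In the first row the result is exactly 28 days old. The rule applies only above 28, so no repeat is triggered and the gap is still 26 days. The same pair of dates also satisfies the 28-day scheduling statement.

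**Does the repeat rule cover the pregnancy test?** The term *safety labs* is not defined.

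- Against: the footnote to inclusion criterion 4 says "Safety labs must be within the normal ranges in" Appendix C, and that appendix lists only blood-count values, PT and aPTT. Section 8.5 says "Safety labs will only be required at screening in the rectal biopsy cohort", whereas every woman of childbearing potential has the pregnancy test whatever her cohort.
- For: Section 6.1.2 mentions urine as well as blood under safety labs. In Section 6.1.3 the asterisk that leads to the rule sits on screening lab evaluations in general, and the rule points to Section 7.2, where the pregnancy test appears.

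The balance favors the narrower reading, but the 26-day figure does not depend on it.

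**The case against.** The strongest opposing case has four parts.

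*The repeat rule may already include the test.* At Visit 00B the only scheduled urine test for women is the pregnancy test, because their gonorrhea and chlamydia screening uses vaginal swabs. Urine safety labs for a woman would then mean the pregnancy test. This is a fair reading, and it leaves the term ambiguous. It lowers the maximum age from 42 to 28 days but does not remove the 26-day gap.

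*The figures are corners of the windows.* This is true. The 26 days need a test on Day -56, and 42 days would also exceed a strict 28-day scheduling limit. Both are maxima. A repeat rule for results older than 28 days does, however, imply that such intervals were foreseen.

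*Pregnancy control is deliberately tied to study product.* Contraception timing and the 24-hour tests fit that view, and Appendix A lists a negative pregnancy test before dose 2 but not before the Visit 6 biopsy. Yet exclusion 24 bars participation, and Section 8.3.3 stops procedures as well as dosing. SAP Table 2 does mark an eligibility check at Visit 00C, but it would rest on the same old result and the subject's own account.

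*No harm is shown.* Section 2.3.1 names no pregnancy-related biopsy risk and expects serious complications in fewer than 1 in 5000. This stands, and it limits how strongly the point can be put. It does not weigh against a non-invasive test in so few women.

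**Conclusion.** The concern holds. As written, the plan permits the baseline biopsy on a pregnancy result up to 42 days old by the visit windows (28 if the repeat rule applies), with as many as 26 of those days covered by neither a repeat test nor required contraception. The calculation assumes no Day 0 and counts only what the plan requires; a woman may use contraception earlier by choice, and the investigator may test at discretion. The number exposed is at most 10 at the Table 1 targets, fewer if some are not of childbearing potential. This is an inexpensive gain in participant protection and does not affect the statistical analysis. The second biopsy is of much less concern: with dose 2 on Day 28 to 30 and Visit 06 on Day 40 to 46, the last negative test is normally 10 to 18 days old and contraception is in force.

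**What to change.** For women of childbearing potential in the biopsy cohort, add a urine pregnancy test at Visit 00C, with a negative result known before the biopsy (for example, within 24 hours before it). Enter it in Protocol Sections 6.1.3 and 7.2.1, the pregnancy row of Appendix A, and SAP Table 2. In Section 6.1.3, state which tests *safety labs* covers, so that site staff apply the 28-day rule in one way.

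The cost is a wording change, one cell in each schedule table, and at most 10 × 1 = 10 urine tests at a visit already held. It adds no visit, staff or invasive procedure. A matching test at Visit 06 would bring the total to 20, but it adds little and need not be pursued.

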6.1.4 Visit 00P, Day -27 to -12, Baseline Rectal Mucosal Biopsy, Telephone Visit

This visit will take place 24-48 hours after the baseline rectal biopsy procedure only for subjects enrolled in the rectal biopsy cohort. The following activities will be performed at Visit 00P.

- Assess all AE/SAEs from the biopsy procedure and record them on the appropriate eCRF.
- Subjects will be reminded not to engage in anal intercourse for 1 week after the rectal biopsy procedure.
- Subjects will be reminded to abstain from receptive anal and/or vaginal intercourse, insertion of anything into their vagina and/or anus, or oral sex for at least 2 days prior to the enrollment/first vaccination visit.

6.2 Enrollment

6.2.1 Visit 01, Day 1, Randomization and First Vaccination, Clinic Visit

The following activities will be performed at the first vaccination visit.

- Reconfirm the subject's willingness to participate before performing any study procedures, including their first vaccination.
- Review eligibility criteria, including results of HIV, RPR, and STI screening lab evaluations, with subjects before the first vaccination to assure continued eligibility.
- Review interim sexual history to identify any new sexual partners since the last screening visit. Subjects that report new sexual exposures should undergo repeat STI screening and enrollment should be deferred until results are available and assure continued eligibility.
- Review medical history and any updates obtained by interview of subjects since the last screening visit (Visit 00A or, if performed, Visits 00B and/or 00C) to assure continued eligibility.
- Review all concomitant medications and recent (within 28 days) vaccinations with subjects before the first vaccination for accuracy and completeness. Any new medications taken since the last screening visit (Visit 00A or, if performed, Visits 00B and/or 00C) will be recorded on the appropriate eCRF and assessed for continued eligibility.
- Review COVID-19 vaccine history to ensure the subject is at least 14 days out from any COVID-19 vaccine before receiving study vaccine.
- Assess all AE/SAEs and record them on the appropriate eCRF.
- Obtain vital signs including oral temperature, blood pressure, and pulse before the first vaccination. Perform a targeted physical examination as needed before the first vaccination, if indicated based on review of complete medical history and updates obtained by interview of subjects since the last screening visit (Visit 00A or, if performed, Visits 00B and/or 00C).
- Perform a urine pregnancy test within 24 hours before first vaccination on all female subjects of childbearing potential. Results must be negative and known before first vaccination.
- Collect blood samples for baseline immunologic assays as described in the Schedule of Events ([Appendix A](#))
- Collect rectal and oropharyngeal mucosal secretion samples for immunologic assays as described in the Schedule of Events ([Appendix A](#))
- From female subjects, collect vaginal mucosal secretion samples for immunologic assays as described in the Schedule of Events ([Appendix A](#))

- Subjects will be enrolled in Advantage eClinical and randomly assigned before the first vaccination.
- Perform pre-administration reactogenicity assessments before the first vaccination to establish baseline. Subjects will then receive a single dose of vaccine via IM injection into the deltoid muscle of the preferred arm. The site of injection (right or left arm) and time of administration will be recorded on the appropriate eCRF.
- Observe subjects in the clinic for ≥ 15 minutes after vaccination to monitor for any acute reactions.
- Evaluate the vaccination site and assess for reactogenicity and AE/SAEs for ≥ 15 minutes after vaccination and before discharge from clinic and record on the appropriate CRF.
- Subjects will enter their reactogenicity information in an electronic memory aid (with a paper back up). Subjects will be provided a thermometer and ruler and will record daily oral temperature, solicited injection site and systemic reactions, any unsolicited AEs, and concomitant medications. Subjects will have their electronic memory aid reviewed with them at their next study visit.

